Here the outcome measured at time t , for subject i , in clinic c is denoted by Y_{cit} . To account for the cluster-randomization this model includes a random effect for each clinic denoted as u_c . In order to allow a general longitudinal correlation and variance structure we use three subject-specific error terms denoted by u_{cit} for $t=0, 3, 6$ months. We assume a general 3×3 covariance model for these error terms to provide maximal validity to inference regarding change over time. To allow for potential non-linear change over time, we will enter time as a nominal variable by including dummy codes for the 3 and 6 month time points represented by the variables (3 months) and (6 months). Intervention main effects and interaction between intervention and time indicators capture the difference between intervention clinics and control clinics at each wave – with β_1 representing the adjusted mean difference across intervention groups at baseline (adjusting for the design variables) -- with $\beta_1 + \beta_4$ representing the adjusted mean difference across intervention groups at 3 months – and with $\beta_1 + \beta_5$ representing the adjusted mean difference across intervention groups at 6 months. Therefore, the primary contrasts are given by with β_4 as the 3-month intervention effect, and β_5 as the 6-month intervention effect. Note that each intervention effect accounts for the potential imbalance of outcomes across the intervention and control groups at baseline due to the small number of clusters (β_1) and this is removed from the cross-sectional mean contrasts at each follow-up time to define the key intervention effect parameters. *DesignVars* denotes a vector of covariates that includes: 1) low vs high fidelity, which must be controlled because it was a design/stratification variable for some clinics, and 2) additional covariates theoretically related to both the primary outcome and the probability of not completing follow-up surveys which will aid in enhancing validity against missing data and improving precision of estimation. Specifically, we will include: 1) worried about not have stable housing in the next two months, 2) being on parole or probation and/or presently awaiting charges, trial or sentencing, 3) opioid craving, 4) pain, 5) Audit-C, 6) provider trust (APAC item #6), and 7) any use of other drugs (dummy coding for each class of drug). The pre-specified primary effect of interest will be β_5 , which represents the difference in change from baseline between intervention and control clinics at 6 months. Table S2 presents a shell table for the primary outcome and Figure 2 presents a shell plot. Table S3 presents a shell table for the secondary outcomes.

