
For the primary outcome (mental health related quality of life [0-100]) we will use a linear mixed model with a normal distribution with a linear link function and model structure given above in Equation 1. For the primary outcome days-using-opioids [0-30] we will modify the above linear mixed model and adopt a similar regression structure using a generalized linear mixed model with binomial distribution logit link function. We will retain the random effect structure to include a random effect for clinic and include the time-specific subject-level error terms to both allow for binomial overdispersion and a general longitudinal covariance over time. For the secondary and exploratory outcomes, appropriate link functions will be used for linear, binary (logit), ordinal (logit), and count (Poisson/negative binomial depending on dispersion) data. For any binary longitudinal outcomes, we will simplify the subject-level random effects to be a simple random intercept due to identifiability (no overdispersion and only correlation).

Effect sizes. Cohen's d effect sizes will be calculated and presented with 95% confidence intervals. Between group effect sizes will be calculated as the model-estimated treatment effect at each time point divided by the pooled, raw baseline standard deviation.

Testing of Multiple Primary Outcomes. The intervention will be interpreted to have been successful if there is a significance group difference between either primary outcome, not necessarily both primary outcomes. Corrections for multiple testing will be computed using a Bonferroni correction for the two multiple primary outcomes and therefore we will use an $\alpha=0.05/2 = 0.025$ to test each primary outcome. All secondary outcomes are exploratory and no multiple testing adjustment will be used. We will present secondary and exploratory outcomes descriptively using a forest plot to illustrate the collection of associations with intervention.

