The DSMB directed the research team to discontinue consenting new patients into the trial for reasons of futility due to the current rate of recruitment. Therefore, we present a revised power analysis calculated before the outcome data are to be unmasked. The revised power analysis is based on the observed number of patients enrolled (n=254), observed number of clinics enrolling ≥ 1 patient (n=28), the observed coefficient of variation (0.97) which represents the variation in cluster sizes, and the Intraclass Correlation Coefficients (ICCs) estimated for interim analysis requested by the DSMB. For the masked interim ICC estimation we used all patient data available on 11/7/2022, including N=191 in the baseline sample and N=155 in the 6-month follow-up sample. We adjusted for treatment group and baseline primary outcomes. We used the jackknife method to compute a standard error by computing ICCs deleting each cluster in turn and then averaging these estimates.¹⁶ For the 6-month follow-up, the opioid use ICC was estimated to be 0.00 (SE= 0.02). For the 6-month follow-up, and the MCS ICC was estimated to be 0.03 (SE=0.09). Based on these estimates, and using a Bonferroni correction to account for multiple outcomes, we will have 80% power to detect a medium effect size of 0.40 for days of opioid use and a medium effect size of 0.46 for MCS. This represents a difference of 2.65 (e.g., 15.00 days compared to 12.3 days) days using opioids and a difference of 6.22 (e.g., 40 compared to 33.8) on the MCS between the intervention and control groups.

7. References

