	Overall n (%) or μ (SD)	Intervention Group n (%) or μ (SD)	Control Group n (%) or μ (SD)
Age (years)			
Are you of Hispanic, Latino/a/e or Spanish origin?			
Yes			
No			
Missing			
Race			
American Indian, Alaska Native, or other Indigenous group			
Native Hawaiian or other Pacific Islander			
African American or Black			
White			
Multi-race			
Another Identity			
Missing			
Current Gender Identity			
Man			
Woman			
Non-binary or gender fluid			
Missing			
Marital Status			
Divorced			
Married or living with a partner			
Separated			
Single, never married			

Missing

Housing Status

No, not living in stable housing

Yes, living in stable housing

Missing

Concern about Future Housing

No, not worried about housing in the near future

Yes, worried about housing in the near future

Missing

Parole/Probation

No

Yes

Missing

Awaiting charges, trial, or sentencing

No

Yes

Missing

Currently mandated by a court to receive addiction treatment

No

Yes

Missing

Individual Readiness to Change (ICR; range: 0-10)

Importance for change

Confidence for change

Readiness for change

Clinical Characteristics:

Veterans Short Form 12 Mental Health Component Summary score

(MCS; range: 0-100)

Opioid Use:

Any opioid use in the past 30 days

Number of days of opioid use in the past 30 days

Opioid Craving:

Not at all

Slightly

Moderately

Considerably

Extremely

Medication for OUD:

Lifetime

Current

Alcohol Use: (AUDIT-C; range: 0-12)

Other Drug Use: Any use in the past 30 days

Cocaine and/or crack use

Other stimulant use

Sedative and/or tranquilizer use

Cannabis use

Inhalant use

Other illegal drug use

Recent Overdose Experience

Ever overdosed

Number of previous overdoses

Overdosed in the past 6 months

Number of overdoses in the past 6 months

Pain Level (PEG; range: 0-10)

Hopkins Symptoms Checklist (SCL-20; range: 0-4)

Anxiety (PROMIS Measure - Anxiety 8a - Adult v1.0: range: 36.4-76.8)

PTSD Checklist (PCL-5; range: 0-80)

Table S2. Multiple primary outcomes across intervention conditions

	Intervention		Control		Treatment Effects		
	Mean (SD)	95% CI	Mean (SD)	95% CI	Adjusted Odds Ratio	95% CI	Cohen's d
Opioid Use							
Baseline							
3 months							
6 months (primary outcome)							
					Adjusted Mean Difference	95% CI	Cohen's d
MCS							
Baseline							
3 months							
6 months (primary outcome)							

Table S3. Treatment effects for secondary and exploratory outcomes at 3 and 6 month follow-up

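### The clinic intercept in Eq. 1 cancels from the primary contrast β5, so the primary test ignores clinic differences in change; if these exist, type I error exceeds 2.5%

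*SAP*

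**What the plan says.** SAP section 4.1, Eq. 1, has one clinic term, u_c, with no time index. The other random terms are three patient-level errors (0, 3 and 6 months) with a general 3×3 covariance. Fidelity and the other covariates enter as main effects only. The text says "To account for the cluster-randomization this model includes a random effect for each clinic". For opioid days the model becomes a binomial logit GLMM, and "We will retain the random effect structure to include a random effect for clinic".

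The primary effect is β5, "which represents the difference in change from baseline between intervention and control clinics at 6 months". The same section describes β1+β5 as "representing the adjusted mean difference across intervention groups at 6 months". Shell Table S2 (SAP section 8) has a row "6 months (primary outcome") under a column headed Adjusted Mean Difference for MCS, which is the section 4.1 term for β1+β5 rather than β5. The SAP's modifications table records that this row was relabelled from a change to a 6-month value.

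SAP section 6 gives 6-month ICCs: "the MCS ICC was estimated to be 0.03 (SE=0.09") and "the opioid use ICC was estimated to be 0.00 (SE= 0.02"). They are not ICCs of change: "We adjusted for treatment group and baseline primary outcomes". Each primary outcome is tested at 0.025, and success on either one is enough.

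**The concern.** Clinics are the randomised units, so the arm difference in change has to be judged against how much clinics vary in change. A clinic effect that is constant over time says nothing about that. When β5 is formed from Y(6) − Y(0), u_c drops out, and any real clinic variation in change is absorbed into the patient covariance and treated as independent between patients. The SE of β5 is then too small.

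Nothing else in the documents supplies the missing error. The random slope in Protocol 9.4.2 is at person level. The sandwich estimator in Protocol 9.4.1 applies only if residuals are non-normal, and no clustering level is stated. The SAP gives no clinic-by-time term, cluster-robust SE or small-sample df rule.

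Because success needs only one of the two outcomes, an inflated MCS test alone could produce a false claim of effectiveness.

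**Working it through.** **Inputs.** From SAP section 6: 254 patients, 28 enrolling clinics, cluster-size CV 0.97, and 191 baseline and 155 six-month records at the interim (36/191 = 19% missing). Alpha is 0.025 (SAP 4.1), two-sided (Protocol 9.4.2). Assumptions: the 19% applies to the final sample (about 206 of 254) and is missing at random, outcome SD is 1, baseline to 6-month correlation is 0.5, and clinics are randomised in pairs.

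**The plan's own figure.** 0.05/2 = 0.025. With no clinic variation in change, 8,000 simulated β5 tests with the normal critical value 2.2414 rejected in 2.6% to 2.7%.

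**Cancellation.** With complete data, Var(β5) = L′ΣL(1/N1 + 1/N0), L = (−1, 0, 1). The clinic variance enters only through L′1 = 0. With the values above, L′ΣL = 1 + 1 − 2(0.5) = 1, and with 127 per arm the SE is √(2/127) = 0.1255. GLS for Eq. 1 gave 0.1256 at every clinic variance from 0 to 1.0. In 5 of 5 simulated data sets, full maximum-likelihood fits of Eq. 1 (no covariates) gave the same β5 and SE, to four decimals, as a two-sample comparison of change scores that ignores clinic.

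With 19% missing at 6 months:

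| Model | Clinic variance | SE of β5 | SE of β1+β5 |
|---|---|---|---|
| MCS (SD units) | constant, 0 to 1.0 | 0.1334 to 0.1335 | 0.133 to 0.417 |
| Opioid logit | constant, 0 to 3 | 0.399 to 0.401 | 0.379 to 0.803 |

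Adding clinic-by-time variance of 0.015 per occasion (ICC of change 0.03/1.03, about 0.03) raises the correct MCS SE of β5 to 0.158, or +18%. Eq. 1 has no term for it.

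**What the SAP's ICC implies.** Let v be the per-time clinic ICC, r the clinic autocorrelation and b the within-clinic patient correlation.

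- Adjusted ICC = v(1+b²−2br) / [v(1+b²−2br) + (1−v)(1−b²)]
- ICC of change = v(1−r) / [v(1−r) + (1−v)(1−b)]

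Set the adjusted ICC to 0.03. At r = 1 the ICC of change is 0. At r = 0 and b = 0.5, v = 0.0182 and the ICC of change is 0.0182/(0.0182 + 0.9818×0.5) = 0.036. For b from 0.3 to 0.7 the r = 0 value is 0.034 to 0.036.

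**Type I error by formula.** DE = 1 + [(CV²+1)m − 1]ρ and error = 2[1 − Φ(2.2414/√DE)], with ρ the ICC of change. At 206 patients, m = 7.36:

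- ρ = 0.03: DE = 1.398, error 5.8%
- ρ = 0.036: DE = 1.478, error 6.5%

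At all 254 patients these become 6.7% and 7.6%. With equal cluster sizes, ρ = 0.03 gives 4.0% to 4.4%.

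**Type I error by simulation, MCS** (10,000 replicates each, 19% missing; u_c left out of the fit because it does not affect β5):

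| ICC of change (assumed) | Normal reference | 26 df |
|---|---|---|
| 0 | 2.9% | 2.1% |
| 0.01 | 3.4% | 2.5% |
| 0.03 | 5.9% | 4.6% |
| 0.036 | 6.6% | 5.1% |
| 0.10 | 14.8% | 12.3% |

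At 0.03, if half or all of the clinic variation is shared within randomisation pairs, the figure is 5.0% or 4.1%. A separate simulation of 8,000 runs gave 5.7% and 6.3% at 0.03 and 0.036 with 206 patients.

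**Opioid use** (binomial-30 logit GLMM, assumed logit mean −3 and SD 2.5, about 800 replicates each, Monte Carlo error up to about 1.4 points): 2.4% at 0, 4.4% at a latent ICC of change of 0.03, 4.1% at 0.05.

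**The case against.** The algebra is hard to dispute; the size is open to challenge.

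- **The inflation is conditional.** An ICC of change of 0.03 or more, given the SAP's 0.03, needs clinic means to be no more stable over six months than one patient's score (r no greater than b). At b = 0.5 and r = 0.8 to 0.9, the ICC of change is 0.020 to 0.013, and the formula at 206 patients gives about 4.7% to 3.9% (normal) or 3.5% to 2.8% (26-df critical value). At r = 1 there is no inflation. This stands, so the size is a range.
- **Reference distribution and stratification.** A 26-df reference and variation shared within health systems both lower the figures. This also stands; the SAP names no reference.
- **No precise full fit of Eq. 1 under inflation.** The full maximum-likelihood run with missing data at 0.03 gave 4.2%, but with only 120 fits (SE 1.8 points) it neither confirms nor refutes the size.
- **Opioid evidence is thin.** The simulated days SD was about 7.7, against 2.65/0.40 = 6.6 implied by SAP section 6, and no trend can be read from the runs. The SAP's estimate is 0.00. The point is therefore mainly about MCS.
- **β5 is explicitly pre-specified, and Table S2 is only a shell.** This is true, but the table is where the primary result will be reported. If it means β1+β5, u_c stays in but baseline imbalance is no longer removed.
- **A sensitivity analysis might be enough.** This does not meet the point: it would leave the success claim resting on a test whose validity depends on an unstated assumption.

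**Conclusion.** The concern holds. As written, the primary test of this cluster-randomised trial allows for no between-clinic variation in change, and the statement that u_c accounts for the cluster randomisation is not true for β5. The cancellation is exact for MCS with complete data, and almost exact with 19% missing and in the opioid logit model.

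The size depends on an ICC of change that the documents do not give. Over 0 to 0.036, the range compatible with the SAP's MCS point estimate, type I error runs from 2.9% to 6.6% (normal) or 2.1% to 5.1% (26 df) against 2.5%. The ICC's SE of 0.09 does not exclude larger values. These figures also rest on the assumed follow-up share, correlation and pairing. For opioid use there may be no inflation. The main analysis must be changed before a success claim rests on it.

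**What to change.** 1. State one primary contrast, and make the β5 definition in SAP 4.1 agree with the 6-month primary row of Table S2.
2. Keep clinic-level error in that contrast by one of: a clinic-by-time random effect in both primary models; a follow-up model with the baseline outcome as covariate and a random clinic intercept; or clinic-level robust or permutation inference that respects the randomisation strata.
3. State a small-sample rule: about 26 df, or Kenward-Roger for MCS. If the opioid GLMM does not converge with the added term, use a clinic-level permutation or bootstrap test.

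In simulation (1,500 replicates per scenario), the clinic-by-time MCS model with REML and 26 df gave type I error of 1.3% to 2.6% for an ICC of change of 0 to 0.036, and 3.1% at 0.10. It can therefore be conservative.

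The cost is an SAP amendment and a re-run of the two primary models, with no new data. If they have already been run, date the change and report both versions. MCS intervals widen by about 5% if clinics do not differ in change, and by about 16% to 18% at 0.03 to 0.036. Some convergence work is likely, since the SAP's modifications table already records a covariate dropped for that reason. The baseline-covariate option replaces the pre-specified difference in change with an adjusted 6-month difference, and the amendment should say so.

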1 PROTOCOL SUMMARY

1.1 SYNOPSIS

Title	Collaborating to Heal Addiction and Mental Health in Primary care (CHAMP)
Grant Number	MH121942
Study Description	The gold-standard intervention for Opioid Use Disorder (OUD) is Medication for Opioid Use Disorder (MOUD). Because more patients with OUD need access to MOUD in primary care, we are testing whether the Collaborative Care model (CoCM) is effective at treating both mental health symptoms (MHS) and OUD concurrently in primary care settings. The intervention is CoCM for MHS and OUD. The active control is CoCM for MHS, but not treating OUD. The primary objective is to compare patient-reported outcomes in the intervention and control groups, and will be tested with in an Effectiveness trial. The secondary objective is to compare the detection of OUD pre- versus post-OUD screening implementation, and will be tested using a Pre-Post trial design. The exploratory objective is to compare intervention clinics randomized to a low-intensity sustainability implementation strategy or a high-intensity sustainability strategy, and will be tested in an Implementation trial.
Objectives	The CHAMP study addresses three important objectives including: Primary Objective - Does implementing Collaborative Care for OUD and MHS improve MHS and OUD outcomes? Secondary Objective - Can OUD screening be effectively incorporated into primary care mental health screening protocols? Exploratory Objective - What implementation strategies are effective at sustaining Collaborative Care programs that concurrently manage mental health disorders and OUD?
Endpoints	The multiple primary outcomes for the Effectiveness trial are self-reported use of opioids and mental health functioning.
Study Population	We will recruit 1,200 adult primary care patients screening positive for OUD and MHS from 42 clinics in 11 states and the District of Columbia. Age, gender and race/ethnicity will be representative of the demographics and epidemiology of the clinics.
Description of Sites/Facilities Enrolling Participants	Sites include a range of primary care settings in the United States. Forty-two clinics from 15 healthcare systems.

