6.3 MEASURES TO MINIMIZE BIAS: RANDOMIZATION AND BLINDING

The Effectiveness and Implementation trials use cluster (site-level) randomization. Sites will be stratified by fidelity and healthcare organization prior to randomization. Those administering the surveys to patients will be masked to randomization status (and site). If survey administrators are inadvertently unmasked, that will be recorded and the rate of unmasking will be monitored. The analysis will examine the potential for bias as a result of making.

Study Multiple PIs will not have access to survey data until the last patient has completed the 6-month follow-up survey. The study statisticians and data analysts will have access to survey data, adverse events and randomization status to generate reports for DSMB meetings.

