In 2018, the National Institute of Mental Health (NIMH) issued a Request For Applications (RFA-MH-19-525) titled “Helping to End Addiction Long-term (HEAL) Initiative: Effectiveness Trials to Optimize, Implement, Scale, and Sustain the Collaborative Care Model for Individuals with Opioid Use Disorders and Mental Health Conditions”. Four clinical trials were funded, including the Collaborating to Heal Addiction and Mental Health in Primary care (CHAMP) trial described in this manuscript. The objective of the CHAMP trial was to compare the effectiveness of a Collaborative Care Model (CoCM) intervention designed to co-manage both Opioid Use Disorder (OUD) and common co-occurring Mental Health Symptoms (MHS) to a usual care control condition representing CoCM designed to manage co-occurring MHS only.

This statistical analysis plan (SAP) will comprehensively enumerate the primary and secondary outcomes, and mediating variables, and corresponding analyses.

2. Study design

The CHAMP hybrid type 2a effectiveness-implementation trial was a cluster randomized trial in which clinics were randomized to CoCM for OUD and MHS or CoCM for MHS only. Hybrid type 2a trials compare two clinical interventions and pilot test a practical, but not evidence-based, implementation strategy.

Randomization - Initially 24 clinics were stratified according to one of two CoCM fidelity cohorts (specified as low or high) and healthcare organization and then randomized in a 1:1 ratio by our statistician into one of two arms (intervention or control). Stratification served two purposes. First, stratifying on healthcare organization (each has 2 or 4 clinics in the study) should balance the intervention and control groups according to key system level factors that influence quality and outcomes (e.g., electronic health record quality). Second, stratifying on cohort ensures balance with regard to fidelity to the CoCM model which is likely to be correlated with our primary outcomes. In addition, clinics with lower fidelity were designated to have a longer training duration. An additional 18 clinics were recruited later during the study and they all received the short training duration in order to maximize recruitment, and therefore we did not stratify the randomization of the additional 18 clinics by fidelity but did continue to stratify by health care system.

3. Outcomes

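### Eq. 1 omits healthcare system, the only factor that stratified all 42 clinics, and its low/high fidelity covariate does not describe how the later 18 were randomised

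*SAP*

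**What the plan says.** SAP section 2 (Randomization) describes two waves. In the first, "Initially 24 clinics were stratified according to one of two CoCM fidelity cohorts (specified as low or high) and healthcare organization". For the second, "we did not stratify the randomization of the additional 18 clinics by fidelity but did continue to stratify by health care system". The purpose given is that "stratifying on healthcare organization (each has 2 or 4 clinics in the study) should balance the intervention and control groups" on system-level influences on quality and outcomes. Protocol 1.1 gives the final count as "Forty-two clinics from 15 healthcare systems", and Protocol 6.3 names both stratifiers: "Sites will be stratified by fidelity and healthcare organization prior to randomization".

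SAP 4.1 then defines the covariate vector. It contains fidelity, justified as "low vs high fidelity, which must be controlled because it was a design/stratification variable for some clinics", and seven patient-level items ending with "6) provider trust (APAC item #6), and 7) any use of other drugs (dummy coding for each class of drug". On clustering, "this model includes a random effect for each clinic". Neither Eq. 1 nor Protocol 9.4.2 has a term for healthcare system, fixed or random, and no reason is given. The pre-specified effect is beta5, the between-arm difference in change from baseline to 6 months.

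For the 18 later clinics the SAP says that all had the short training duration. It does not say whether they count as low fidelity, high fidelity or neither.

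**The concern.** The plan's reason for adjusting for fidelity applies with more force to healthcare system, which shaped the allocation of every clinic and was chosen because it is expected to influence outcomes. A model that leaves out a balanced stratifier can report a standard error that does not match the design. With 254 patients in 28 enrolling clinics there is little precision to spare.

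The fidelity covariate raises a second, smaller matter. A two-level variable cannot represent 18 clinics that were never stratified on it. Two analysts could code them differently and both claim to follow the SAP.

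**Working it through.** **1. Stratifiers against model terms.** From SAP section 2, 24 + 18 = 42, which matches Protocol 1.1.

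| Factor | Clinics stratified on it | In Eq. 1? |
|---|---|---|
| Healthcare system | 42/42 (100%) | No |
| Fidelity | 24/42 (57%); not 18/42 (43%) | Yes, two levels |

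**2. What beta5 uses.** Subtracting baseline from 6 months in Eq. 1, for patient i in clinic c:

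Y(6) − Y(0) = beta3 + beta5 × Intervention + u_ci6 − u_ci0

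The clinic term u_c has no time index, so it drops out, and any constant system effect inside it drops out too. This is exact for the linear MCS model with complete data. It is not exact with missing follow-up, or for opioid days under the logit model.

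**3. A baseline-adjusted 6-month comparison.** Inputs from SAP section 6: N = 254, 28 clinics, cluster-size CV 0.97, ICC 0.03 (SE 0.09) for MCS and 0.00 (SE 0.02) for opioid use. Assumption: a share s = 0.5 of the clinic variance lies between systems. Mean cluster size m = 254/28 = 9.07.

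With equal clusters and full arm balance within systems, the variance ratio is [ICC(1−s) + (1−ICC)/m] / [ICC + (1−ICC)/m].

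- ICC 0.03: (0.015 + 0.1069)/(0.030 + 0.1069) = 0.890; SE falls 5.6%
- ICC 0.05: (0.025 + 0.1047)/(0.050 + 0.1047) = 0.838; SE falls 8.4%
- ICC 0.10: (0.050 + 0.0992)/(0.100 + 0.0992) = 0.749; SE falls 13.5%

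These are upper values, because enrolment was neither equal nor complete. I therefore computed generalised least squares SEs with known variance components. Twenty-eight of the 42 clinics were drawn at random, with CV near 0.97. The layout is assumed: nine systems of 2 clinics and six of 4 (9×2 + 6×4 = 42), half in each arm. Averages over draws, in outcome SD units:

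| ICC | SE reported, clinic term only | True SE of that estimate | SE with system term | Fall in reported SE | Efficiency gain |
|---|---|---|---|---|---|
| 0.03 | 0.1517 | 0.1468 | 0.1460 | about 4% | 0.5% |
| 0.05 | 0.1639 | 0.1562 | 0.1547 | about 6% | 0.9% |
| 0.10 | 0.1885 | 0.1750 | 0.1718 | about 9% | 1.8% |

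Most of the fall lies between the reported and the true SE of the same estimate. At ICC 0.00 every difference is zero.

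**4. The change contrast when effects act after baseline.** Assume a clinic-by-time and a system-by-time variance of 0.015 each, and a patient change variance of 1 (baseline to follow-up correlation 0.5). Eq. 1 has nowhere to put these effects except the patient errors, which it treats as independent between patients. Its SE is then about √(4 × 1.03/254) = 0.127 with equal arms. Averaged over unequal layouts it is 0.128, against a true SE of 0.149; a repeat with fresh draws gave 0.130 and 0.151. The reported SE is too small by 1 − 0.128/0.149 = 14%. By normal approximation the critical value 2.241 acts as 2.241 × 0.128/0.149 = 1.93, a two-sided level of about 0.054 instead of 0.025.

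The clinic-by-time part adds about 4 × 0.015 × 9.07 × (1 + 0.97²)/254 = 0.0042 to the variance. The total excess is 0.149² − 4/254 = 0.0065. So about two thirds comes from clinic-by-time and one third from system-by-time.

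**5. Fixed system dummies.** Simulations with 28 clinics in 15 systems, effect 0.46 and alpha 0.025 compared no system term with 14 dummies. The dummies lowered power in five of six scenarios, for example 75% to 58% (system ICC 0.03, clinic ICC 0) and 87% to 61% (change scores, constant system effect). They helped only at system ICC 0.10 (54% to 59%).

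**The case against.** The strongest reply is that the planned contrast already removes the problem: the clinic term is constant over time, so constant system variance does not reach beta5 for MCS. This stands, and the SE reductions in step 3 therefore do not apply to beta5 as written. The same argument covers the fidelity covariate, which enters only as a main effect.

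Three more points stand. No passage reports a system effect acting after baseline, so step 4 is conditional. The opioid-use ICC estimate leaves nothing to recover for that outcome. Adding terms to a binomial mixed model that already has a clinic effect and a general 3×3 patient covariance is not free, and the SAP's change log shows a covariate dropped to help convergence.

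It could also be said that omitting system only makes the test conservative. Simulated type I error without a system term, where system variance was present, was 0.007 to 0.017 against 0.025. That holds for a single time point, and for change scores fitted with their own clinic intercept. Eq. 1 has no clinic effect on change, so these runs do not vouch for beta5.

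A reader might infer that the omission makes the primary SE too large and wastes the precision gained by stratifying. The documents do not support that for beta5: constant effects cancel, and effects acting after baseline push the SE the other way. A reader might also infer that including fidelity is an error. It is not, because fidelity stratified 24 clinics and the SAP says so openly.

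**Conclusion.** The inconsistency is established from the text: the SAP states a rule for stratifiers, applies it to the partial one and leaves out the universal one without explanation. The fidelity coding is undefined for 18 of 42 clinics.

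The statistical consequence is modest and depends on the contrast. In a baseline-adjusted 6-month analysis the reported SE would fall about 4% to 9% over ICC 0.03 to 0.10, with a real efficiency gain of 0.5% to 2%. This rests on half the clinic variance lying between systems and on an assumed layout of clinics over systems. For beta5 the omission is nearly harmless for MCS if system effects are constant. If effects act after baseline the Eq. 1 SE is too small, by about 14% at the assumed variances, with clinic-by-time the larger contributor. The documents give no estimate of those variances, so this is a vulnerability and not a demonstrated inflation of false positives. The point merits a SAP change but does not by itself invalidate the primary analysis.

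**What to change.** - **System term.** Add a random effect for healthcare system. Use a random intercept if follow-up is modelled with baseline as a covariate. If beta5 is kept, use a system-by-time random effect together with a clinic-by-time one; a constant system intercept would do almost nothing there. Do not use 14 fixed dummies.
- **Fidelity.** Replace the low/high covariate by three levels: first-wave low, first-wave high, and second-wave (not stratified on fidelity).
- **Convergence rule.** State in advance that the system term is dropped from the binomial model for opioid days if that model does not converge, and that the result is reported as such.

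The cost is SAP wording and extra variance components: one with a random intercept, more with time-varying effects. With 28 enrolling clinics they may be estimated at zero, or may strain the binomial model.
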